2.6 ANALYSIS OF PHARMACODYNAMIC VARIABLES

All the pharmacodynamic analyses will be performed using the pharmacodynamic population.

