#### 10.1.2 Assessment methods

All eligible patients will have hemoconcentration samples obtained and total body water (deuterium oxide) assessment performed as per [Section 10.1.2.1](#) below.

Sites that have the capacity to perform the additional plasma volume assessment by the I-albumin method will follow the procedure described in [Section 10.1.2.2](#).

Patients who decline measurement of total body water or plasma volume by the indicator dilution methods, or in cases where in the opinion of the Investigator technical issues might prevent successful completion of those techniques, may still participate in the study provided they have measurements of plasma volume by the indirect hemoconcentration method.

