### **13.1.3.5 Visit 5 (Day 14±1)/**

Discharged Patients will return to the clinical site on day 14 ± 1 (Visit 5;). Exceptions can be made for those patients who may have been transferred to a step down unit, or rehabilitation ward or a different hospital. In those cases, plasma volume will not be assessed by the radiolabeled albumin method, unless the place is authorized for administration and collection of radioactive samples (such as a nuclear medicine facility) and has been discussed and approved by the relevant authority of the Institution(s) and Sponsor.

On days of site visits patients should be instructed not to take their dose of IMP in the morning of that day, as this will be administered by site staff as per the period flow chart in [Section 1.3](#).

The guidelines described above for Day 1 procedures and discharge, should also apply on day 14. Please refer to the study flow chart in [Section 1.2](#) and the period flow chart in [Section 1.3](#).

A patient who had plasma volume assessment performed on Visit 2 (Day 1) by the I-albumin method, should also have plasma volume assessment performed on Visit 5 by the I-albumin method (Day 14 ± 1).

A patient who *did not* have plasma volume assessment performed on Visit 2 (Day 1) by the I-albumin method, need *not* have plasma volume assessment performed on Visit 5 (Day 14 ± 1).

Patients should bring their Diaries, and relevant information will be transcribed to the eCRFs. New diaries will be dispensed.

The technique for measuring BP will be reviewed and further training provided as appropriate.

The Investigator will assess compliance with IMP.

IRT will be notified for end of treatment (EOT).

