#### **14.3.3 Pharmacodynamic (PD) population**

For the main PD endpoints of plasma volume and hemoconcentration, the PD population will consist of all randomized and treated patients who have valid values of the main PD parameters both at baseline and at Day 14/EOT.

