2.2.1 Pharmacodynamic population

For the main PD endpoints of plasma volume and hemoconcentration, the PD population will consist of all randomized and treated patients who have valid values of the main PD parameters both at baseline and at Day 14/EOT.

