2.6.1 Description of pharmacodynamic variables

The following pharmacodynamic variables will be analyzed:

Primary PD variables

- Change in hemoconcentration from baseline to D14/EOT as assessed by changes in hematocrit, hemoglobin, albumin and total protein.
- Change in plasma volume in milliliters from baseline to D14/EOT as assessed by the indicator dilution method using ¹³¹I-labelled human albumin.

Secondary PD variables:

- Change in erythropoietin (mU/ml) from baseline to D14 measured by chemiluminescent enzyme-labelled immunometric assay
- Change in NT-proBNP (pg/mL) from baseline to D14 measured by standard electrochemiluminescence immunoassay

Other Exploratory PD endpoints

- Change in total body water (mL) from baseline to D14 as assessed by the indicator dilution method using deuterium oxide
- Change in uric acid (mg/dL) from baseline to 14 days as measured by standard assay
- Change in beta-hydroxybutyrate (μM) from baseline to 14 days as measured by standard enzymatic colorimetric assay
- Change in red cell mass (mL) from baseline to D14, as derived from measurements of plasma volume (assessed by the indicator dilution method using ¹³¹I-labelled human albumin) and hematocrit
- Change in total blood volume (mL) from baseline to 14 days, as assessed by the indicator dilution method using ¹³¹I-labelled human albumin
- Percentage of patients within 15% of ideal blood volume on study day 14
- Blood pressure (sitting, SBP and DBP) at day 14, compared to baseline

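### The SAP runs every PD analysis on a population defined only for plasma volume and hemoconcentration; on its natural reading, a missing optional tracer pair removes complete pairs on other endpoints

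*SAP*

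**What the plan says.** **Which population is used.** SAP 2.6: "All the pharmacodynamic analyses will be performed using the pharmacodynamic population". SAP 2.6.1 lists as PD variables the two primary measures and also erythropoietin, NT-proBNP, total body water, uric acid, beta-hydroxybutyrate, red cell mass, total blood volume, the ideal-blood-volume percentage and sitting blood pressure. The sentence therefore covers all of them.

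**How it is defined.** SAP 2.2.1 opens "For the main PD endpoints of plasma volume and hemoconcentration" and admits "all randomized and treated patients who have valid values of the main PD parameters both at baseline and at Day 14/EOT". It defines no set for the secondary or other endpoints. Protocol 14.3.3 has the same definition, but the protocol has no sentence extending it to every PD analysis.

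**What plasma volume means here.** SAP 2.6.1: "Change in plasma volume in milliliters from baseline to D14/EOT as assessed by the indicator dilution method", with 131I-labelled albumin as the indicator.

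**When the tracer is measured.** Protocol 10.1.2 and 10.1.2.2 restrict it to sites that have the capacity. Under 10.1.2, patients who decline it, or for whom technical problems are foreseen, "may still participate in the study provided they have measurements of plasma volume by the indirect hemoconcentration method". For patients transferred before Visit 5, Protocol 13.1.3.5 says "plasma volume will not be assessed by the radiolabeled albumin method, unless the place is authorized". The same section does not require a Day 14 measurement from a patient who had none on Day 1.

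**Model and missing data.** SAP 2.6.2 uses baseline plasma volume as the ANCOVA covariate, and 2.6.3 fits similar models to the secondary and other endpoints. SAP 2.9 does not replace missing post-baseline values.

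**The concern.** The protocol deliberately keeps patients who cannot or will not have the tracer. Hemoconcentration samples are planned for all eligible patients, and the flow charts schedule the biomarkers on Days 1 and 14 with no site-capacity condition. The SAP then appears to make inclusion in every PD analysis depend on the tracer, a measurement that NT-proBNP, erythropoietin and most other endpoints do not need.

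Precision on both secondary endpoints is at stake, and so is precision on hemoconcentration, which is a primary PD variable. If tracer pairs are lost through events after randomization, so is the comparability of the arms. Replacement does not repair this: Protocol 8.1 and 12.3 replace patients who end treatment early, not treated patients who lack a tracer pair.

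**Working it through.** **1. The plan's own figures.** The SAP 1.3 power calculation counts patients with plasma volume at both visits. With a difference of 9/10 × 0.47 L = 0.423 L, SD 0.8 L and one-sided alpha 0.05, an exact t-test gives 71.9% power for 54 versus 27 (71% stated) and 60.4% for 40 versus 20 (60% stated). Those figures reproduce and are not in dispute. Protocol Table 6 plans 6 + 6 = 12 tracer samples per patient; 12 × 64 = 768, as stated.

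**2. Reading the rule.** Take a patient with hemoconcentration, NT-proBNP and erythropoietin on both days and no tracer pair.

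- SAP 2.2.1 names two main endpoints and asks for valid main parameters in the plural. SAP 1.2.1 describes direct and indirect methods together. Read this way, the patient lacks one required parameter and is outside the PD population.
- SAP 2.6 then excludes the patient from every PD analysis, and SAP 2.9 offers nothing to bring the patient back.

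**3. Size of the loss.** Let m be the share of patients without a tracer pair. The documents do not give it, so it is assumed here. N is the current protocol's 64 (37 active, 27 placebo, from Protocol Table 1), and all 64 are taken to have complete pairs on the other endpoint.

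Patients kept = 64 × (1 − m). Standard-error factor = 1/√(1 − m).

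| m | Kept of 64 | SE factor |
|---|---|---|
| 0% | 64 | 1.000 |
| 10% | 57.6, about 58 | 1.054 |
| 20% | 51.2, about 51 | 1.118 |
| 30% | 44.8, about 45 | 1.195 |
| 40% | 38.4, about 38 | 1.291 |

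As a cross-check, rounding each arm separately and using t quantiles keeps 57, 52, 45 and 38 patients. The 90% interval half-widths grow by about 6%, 11%, 20% and 31%.

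**4. Would redefining the population be enough?** No. If baseline plasma volume stays as the covariate in the secondary models, a patient without a Day 1 tracer value still drops out of the ANCOVA. Only the descriptive summaries would regain that patient.

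**5. How tracer pairs go missing.** Site capacity and refusal act mainly from Day 1, so they mostly cost precision. Transfer before Day 14 to a place not authorized for the tracer happens after randomization, so it could also introduce selection.

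**The case against.** The strongest reply is that exclusion is one reading and not a stated rule. SAP 2.2.1 never says outright that both parameters are needed in every patient. Protocol 5.1 joins the direct and indirect methods with and/or, and Protocol 10.1.2 treats hemoconcentration as an indirect measure of plasma volume. If either method suffices, patients without the tracer stay in the population. This stands as a limit on certainty. It does not rescue the text: two programmers could build different sets, and the secondary endpoints would still have no population of their own.

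Table 6 also counts. A tracer pair is budgeted for every patient, so the loss could be negligible. It is weak evidence of coverage, though, because it budgets deuterium for all 64 as well, which patients may also decline. Table 12 marks the tracer row as conditional.

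A reader might infer three stronger points that the documents do not support:

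- **Blood-pressure data are lost.** They are not. SAP 2.7 and 2.7.3 summarise them on the safety population, so only the PD analysis of blood pressure is affected. SAP 2.9 also lists all individual data.
- **The patients removed are mainly transferred patients who are less well.** Nothing shows that transfer is the main route or that transferred patients are sicker. Protocol 13.1.3.4 notes that long hospital stays can follow from local policy.
- **The loss is known to be large.** No share is stated anywhere.

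Finally, SAP 2.6.2 calls the study exploratory and applies no multiplicity control. That lowers the stakes, but it is no reason to set aside complete pairs.

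**Conclusion.** The point holds as a defect of definition. A population written for two main endpoints is applied to all PD endpoints. On its most natural reading, an optional measurement then decides who enters analyses that do not use it. The cost runs from nothing, if every patient has a tracer pair, to a standard error about 29% larger with about 38 of 64 patients, if 40% lack one. That range rests on an assumed share, on otherwise complete pairs, and on both main parameters being required. Selection is possible through the transfer route; its presence and direction cannot be established from the documents. The correction should be made before database lock because it is specific and needs no new data.

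**What to change.** **SAP 2.2.1 and 2.6.** Define the PD-evaluable set separately for each endpoint: every randomized patient who took study drug and has a valid baseline and Day 14/EOT value of that endpoint's own parameter. Require the tracer pair only for plasma volume, total blood volume and red cell mass. Require a valid Day 14 tracer value for the ideal-blood-volume endpoint.

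**SAP 2.6.2 and 2.6.3.** In each ANCOVA, use the endpoint's own baseline as covariate in place of baseline plasma volume. The plasma volume model is unchanged, and patients without a baseline tracer value stay in the other models. Protocol 14.7.3 specifies the plasma volume covariate, so record the change in SAP 1.5.

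**Cost.** SAP wording and programming only. N will differ by endpoint, so each table should show its own N.

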2.6.1 Description of pharmacodynamic variables

The following pharmacodynamic variables will be analyzed:

Primary PD variables

- Change in hemoconcentration from baseline to D14/EOT as assessed by changes in hematocrit, hemoglobin, albumin and total protein.
- Change in plasma volume in milliliters from baseline to D14/EOT as assessed by the indicator dilution method using ¹³¹I-labelled human albumin.

Secondary PD variables:

- Change in erythropoietin (mU/ml) from baseline to D14 measured by chemiluminescent enzyme-labelled immunometric assay
- Change in NT-proBNP (pg/mL) from baseline to D14 measured by standard electrochemiluminescence immunoassay

Other Exploratory PD endpoints

- Change in total body water (mL) from baseline to D14 as assessed by the indicator dilution method using deuterium oxide
- Change in uric acid (mg/dL) from baseline to 14 days as measured by standard assay
- Change in beta-hydroxybutyrate (μM) from baseline to 14 days as measured by standard enzymatic colorimetric assay
- Change in red cell mass (mL) from baseline to D14, as derived from measurements of plasma volume (assessed by the indicator dilution method using ¹³¹I-labelled human albumin) and hematocrit
- Change in total blood volume (mL) from baseline to 14 days, as assessed by the indicator dilution method using ¹³¹I-labelled human albumin
- Percentage of patients within 15% of ideal blood volume on study day 14
- Blood pressure (sitting, SBP and DBP) at day 14, compared to baseline

2.6.2 Primary analysis

The main pharmacodynamic variables, change from baseline to Day 14 in hemoconcentration and plasma volume, will be analyzed using an analysis of covariance (ANCOVA) model with fixed terms for treatment and stratification factor of baseline patient status (diabetic, non-diabetic, ejection fraction status (reduced-preserved), and with baseline plasma volume as covariate. An estimate for the between-group difference in treatment mean changes and corresponding 2-sided 90% confidence interval (CI) will be calculated from the model. The main treatment comparison will be between the pooled treatment (200 mg and 400 mg) group and placebo which will be made at 1-sided $\alpha=0.05$ (or equivalently, 2-sided $\alpha=0.10$).

No multiplicity procedures will be applied as the study is exploratory in nature.

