**10.1.2.1 Hemoconcentration and Total Body Water estimation procedure on Day 1 and Day 14:**

Hemoconcentration will be determined as previously described (22)(23), at all sites.

A new 18 or 20-gauge IV will be placed in a large vein, ideally the antecubital position, on the morning of day 1 and 14. Baseline urine, plasma and serum samples will first be collected.

All patients must have completed the last planned IV bolus or infusion therapy with diuretics.

It is recommended that procedures commence in the morning of D1. The actual start time may vary. The times provided below in Table 3 are indicative.

Total body water measurement, by the deuterium oxide dilution method, will also take place at all sites. Intake of the deuterium oxide solution will take place immediately after completion of the physical exam and baseline specimens at T0 (approximately 7:30 AM). One sample for measurement of deuterium concentration will be collected at baseline and the second one will be collected approximately 3.5 ( ± 10 min) hours after ingestion of the deuterium oxide solution.

At approximately 8 AM the subject will be asked to assume a semi recumbent position that will be comfortable to them for the next one and a half hours. The angle of the bed or chair should be at approximately 45° and will be recorded. At approximately 9:00 AM (after approximately one hour of recumbency) the blood samples for hematocrit, hemoglobin, albumin and total protein will be collected. The arm that the blood samples are being drawn from will not be in a dependent position and will be as close to the level of the right atrium as possible (to prevent hemoconcentration in the arm which can introduce substantial inaccuracy in the measurements).

At approximately 10:00 AM the patient will receive the IMP. At approximately 11:00 AM, a blood sample for deuterium oxide determination will be obtained.

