### 10.1.2.2 Plasma volume procedures on Day 1 and Day 14:

The procedure for plasma volume determination by the  $^{125}\text{I}$ -albumin method will be performed at all sites with the capacity to do so.

The overall procedure and documentation are very similar to those described above, in [Section 10.1.2.1](#). The schedule of events for  $^{125}\text{I}$ -albumin IV administration, including the relevant sampling time points is as described below in [Table 4](#). All times shown are indicative.

Intake of deuterium oxide will take place immediately after completion of the physical exam and baseline specimens at T0 (approximately 7:30 AM). The post-equilibration sample should be collected 3.5 hrs (± 10 min) following administration of the deuterium oxide solution.

At approximately 9:00 AM (after one hour of recumbency), and immediately after the samples for ‘hemoconcentration’ have been obtained, the patient will receive the  $^{125}\text{I}$ -albumin injection. Further blood samples will be collected at 9:12 AM and then every 6 minutes for a total of 6 blood draws (including baseline). Samples should be collected as close to the specified time intervals as possible, however, small deviations (+/- 2 minutes) are acceptable as long as the actual time the sample collected is accurately recorded. A further sample for hematocrit determination will also be obtained at 9:36 AM, together with the final sample for  $^{125}\text{I}$ -albumin determination.

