### 14.7.3 Secondary analysis/analysis of secondary variables

Descriptive statistics for all secondary and other pharmacodynamic endpoints, as raw data and change from baseline will be provided by treatment. Similarly time profile plots of mean  $\pm$  SEM will be provided by treatment for all secondary and other pharmacodynamics endpoints.

For exploratory purposes, the main pharmacodynamic variables, change from baseline to Day 14 in hemoconcentration and plasma volume, will be analyzed using an analysis of covariance (ANCOVA) model with fixed terms for treatment and stratification factor of baseline patient status (diabetic, non-diabetic, ejection fraction status (reduced-preserved), and with baseline plasma volume as covariate. An estimate for the between-group difference in treatment mean changes and corresponding 2-sided 90% confidence interval (CI) will be calculated from the model. The main treatment comparison will be between the pooled treatment (200 mg and 400 mg) group and placebo which will be made at 1-sided  $\alpha$  0.05 (or equivalently, 2-sided  $\alpha$  0.10).

Similar ANCOVA models will be fitted for the secondary and other pharmacodynamic variables or endpoints.

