2.9 DATA HANDLING CONVENTIONS

This section describes the rules and conventions used in the presentation and analysis of data.”

In the in-text and appendices tables, the following treatment labels will be used:

- Placebo
- Sotagliflozin 200mg
- Sotagliflozin 400mg

All individual data for all included subjects will be presented in data listings, sorted by treatment group, subject number, visit and time of measurement.

For parameters with evaluations before administration and in cases of rechecked value(s) for one subject, only the last observation will be used as baseline in descriptive statistics and derivations of other parameter values.

After baseline, only observations planned in the protocol will be used in descriptive statistics.

For clinical laboratory parameters with nonnumeric values, the imputed values used for the descriptive statistics and/or the flags will be determined by considering the following rules:

- If database value is ‘ < X’, the value used will be $X/2$
- If database value is ‘ > X’, the value used will be $X + 10^{[-\text{number of digits of the considered parameter in the database}]}$
- if database value is a range (eg, ‘X – Y’), the values used will be $(Y + X)/2$

If not otherwise stated in the statistical section of the protocol:

- Missing data other than protocol-planned baseline values will not be replaced.

- Descriptive statistics for quantitative parameters will be provided using number of observations (N), mean, standard deviation (SD), standard error of the mean (SEM), minimum, maximum and median.
- Descriptive statistics for qualitative parameters will be provided using frequencies (N) and percent (%).

Handling missing data for adverse events

In case of missing or inconsistent information, an adverse event (AE) will be counted as a treatment-emergent adverse event (TEAE), unless it can clearly be ruled out that it is not a TEAE (eg, by partial dates or other information).

If the start date (or time) of an AE is incomplete or missing, then the AE will be considered as a TEAE unless a partial date (or time) or comment shows it as a pre- or post-treatment event.

If relationship to study drug is missing, the AE will be assessed as unrelated if it started before administration of study medication; in all other cases it will be assumed to be related.

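### The hemoconcentration ANCOVA adjusts for baseline plasma volume instead of the marker's own baseline, and as written drops patients with no baseline ¹³¹I-albumin value

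*SAP*

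**What the plan says.** SAP 2.6.2 (Primary analysis) gives a single ANCOVA for both main PD variables. Its terms are treatment, diabetic status and "ejection fraction status (reduced-preserved), and with baseline plasma volume as covariate". No baseline hematocrit, hemoglobin, albumin or total protein appears. Protocol 14.7.3 has the same model but opens it with "For exploratory purposes, the main pharmacodynamic variables, change from baseline to Day 14 in hemoconcentration and plasma volume". The protocol's own primary PD analysis (14.7.2) is descriptive.

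SAP 2.6.1 defines the plasma-volume variable as "Change in plasma volume in milliliters from baseline to D14/EOT as assessed by the indicator dilution method using" ¹³¹I-labelled albumin. It defines no baseline plasma volume obtained indirectly.

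The two measurements differ in availability:

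- Hemoconcentration (Protocol 10.1.2.1): "Hemoconcentration will be determined as previously described (22)(23), at all sites".
- ¹³¹I-albumin (Protocol 10.1.2.2): the "method will be performed at all sites with the capacity to do so".
- Opting out (Protocol 10.1.2): "Patients who decline measurement of total body water or plasma volume by the indicator dilution methods", or for whom technical problems are expected, "may still participate in the study provided they have measurements of plasma volume by the indirect hemoconcentration method".

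Protocol 13.1.3.5 also provides for patients who had no ¹³¹I test on Day 1.

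On missing data, SAP 2.9 says: "Missing data other than protocol-planned baseline values will not be replaced". It gives no method for replacing a baseline value. SAP 2.6.3 extends similar models to the secondary and other PD variables without restating the covariate.

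**The concern.** Two separate problems follow from one phrase.

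First, a standard ANCOVA omits any record with a missing covariate. The protocol created the hemoconcentration route for patients who cannot or will not have ¹³¹I-albumin. The hemoconcentration model as written needs a ¹³¹I value and so leaves those patients out of its adjusted estimate.

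Second, in an analysis of change, the covariate that usually explains most residual variance is the baseline of the variable itself. Here it is missing for all four markers, even when every patient has ¹³¹I data.

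The stake is precision, and how far the estimate represents the patients enrolled. A covariate that is missing before dosing does not by itself bias the comparison of randomised arms. The plasma-volume model is unaffected because there the named covariate is its own baseline.

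A related but conditional point concerns SAP 2.2.1, which asks for valid values of the main PD parameters at both visits. If that means both main endpoints together, a missing Day 14 ¹³¹I value would also exclude a patient from the hemoconcentration analysis. Protocol 13.1.3.5 allows for this after transfer to another unit.

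**Working it through.** **The plan's own figure.** SAP 1.3 states 71% power with 81 patients and 60% with 60. With a difference of 0.47 × 9/10 = 0.423 L, SD 0.8 L, one-sided α 0.05 and pooled sotagliflozin v placebo (54 v 27; 40 v 20), a noncentral t calculation gives 71.9% and 60.4%. Both reproduce. They concern plasma volume, so they neither support nor weaken this point.

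**Does the written model drop patients?** In a simulated set of 64 patients, 19 had baseline plasma volume removed. The model with the marker's own baseline used 64 records; the model with baseline plasma volume used 45.

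**Cost of case loss.** Inputs are 37 sotagliflozin (10 + 27) and 27 placebo, from Protocol Table 1, and an assumed share f with a baseline ¹³¹I value. The documents give no f.

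- SE inflation = 1/√f
- SE of the difference, in residual SD units = √(1/(37f) + 1/(27f))
- 90% CI half-width = t(0.95, n − 5) × SE. The five parameters are intercept, treatment (pooled v placebo), diabetic status, ejection-fraction status and covariate.

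| f | n = 64f | SE inflation | SE | 90% half-width |
|---|---|---|---|---|
| 1.0 | 64 | 1.000 | 0.253 | 0.423 |
| 0.8 | 51.2 | 1.118 | 0.283 | 0.475 |
| 0.6 | 38.4 | 1.291 | 0.327 | 0.553 |
| 0.5 | 32 | 1.414 | 0.358 | 0.610 |

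**Cost of the covariate choice with nobody lost.** Let ρ be the marker's baseline-to-Day-14 correlation (equal variances), and c the correlation of baseline plasma volume with change in the marker. In units of the marker variance:

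- Variance of change = 2(1 − ρ)
- Residual after the marker's own baseline = 1 − ρ²
- Residual after baseline plasma volume = 2(1 − ρ)(1 − c²)
- SE ratio, own baseline to written model = √[(1 + ρ) / (2(1 − c²))]

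If plasma volume relates to change only through the baseline marker, with correlation r between the two baselines, then c² = r²(1 − ρ)/2. For example, ρ = 0.5 and r = 0.5 give c² = 0.25 × 0.5/2 = 0.0625, and the ratio is √(1.5/1.875) = 0.894.

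| | ρ = 0.5 | ρ = 0.7 | ρ = 0.8 |
|---|---|---|---|
| absolute r = 0.5 | 0.894 | 0.940 | 0.961 |
| absolute r = 0.7 | 0.925 | 0.958 | 0.973 |
| absolute c = 0.3, any path | 0.908 | 0.966 | 0.994 |
| absolute c at which the gain is zero, √((1 − ρ)/2) | 0.500 | 0.387 | 0.316 |

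A simulation of 4000 trials (37 v 27) gave 0.894 for ρ = r = 0.5 with no direct effect, and 1.006 at the break-even c = 0.5. With wider assumptions (ρ 0.5 to 0.9, absolute r 0 to 0.5), the written model's SE is 2% to 15% larger than with the marker's own baseline. None of ρ, r or c is in the documents.

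**The case against.** **Coverage may be complete.** Protocol Table 6 budgets ¹³¹I samples for all of about 64 patients, and SAP 1.3 counts completers with plasma volume at both visits. The Cohort 3 design label in Protocol 1.1 shows plasma-volume sampling on Days 1 and 14, and that cohort is 34 of 64 patients (53%). If Cohort 3 is measured as planned, coverage of 50% would need losses there too. This stands: case loss is possible, not shown, and the 50% row is an extreme. The opt-outs in Protocol 10.1.2 still mean that full coverage is not assured.

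**SAP 2.9 exempts planned baselines from its no-replacement rule.** True, but it gives no method, and a patient never injected has no earlier value to carry in.

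**The PD population may be the real cause.** If SAP 2.2.1 requires both endpoints, patients without ¹³¹I are excluded before any model is fitted, and changing the covariate alone recovers nobody. This is correct, so both edits are needed. Under either reading the same patients are missing from the hemoconcentration ANCOVA.

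**Hemoconcentration may be a calculated percentage volume change.** Protocol 10.1.1.1 cites a published calculation of that kind, and such a variable has no marker baseline of its own. However, SAP 2.6.1 lists four markers, each measured on Day 1, so an own-baseline covariate is defined for them.

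**The analysis is exploratory.** The protocol says so, and the covariate removes nobody from descriptive summaries. That limits the weight. But the SAP makes this model its primary PD analysis, with a 90% CI and a one-sided 0.05 comparison.

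**Conclusion.** The concern holds. The written hemoconcentration model leaves out the analysed marker's own baseline and excludes patients without a baseline ¹³¹I-albumin value.

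The size depends on figures the documents do not give. Case loss costs nothing at full coverage, and 12%, 29% or 41% in standard error at assumed coverage of 80%, 60% or 50%. The covariate choice costs a further few percent under most plausible correlations, and nothing if baseline plasma volume predicts change strongly enough by itself.

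No bias is claimed. The point should be fixed because the repair is nearly free, but it does not threaten the trial's main conclusions. The ambiguity in SAP 2.2.1 is a secondary matter, and the conclusion does not depend on how it is read.

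**What to change.** 1. In SAP 2.6.2 and 2.6.3, make the covariate the baseline value of the variable analysed: baseline hematocrit, hemoglobin, albumin or total protein for the respective marker, and baseline plasma volume only in the plasma-volume model.
2. Keep a hemoconcentration model that adds baseline plasma volume, if wanted, as a sensitivity analysis in patients with ¹³¹I data.
3. In SAP 2.2.1, define the PD population per endpoint: randomised, treated, with valid baseline and Day 14/EOT values for that endpoint. Report N by endpoint and arm.
4. Record the change in SAP 1.5 before database lock.

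The cost is a few sentences in the SAP and no new data. Matching edits to Protocol 14.3.3 and 14.7.3 need an amendment with ethics approval (Protocol 18) and can wait for the next one. The drawback is that N will differ between endpoints, so the direct and indirect results will describe overlapping but not identical patients.
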